### **10.4 Monitoring, Quality Assurance, and Inspection by Health Authorities**

This trial will be monitored in accordance with the ICH GCP and any other applicable regulations. The site Monitor will perform visits to the trial site at regular intervals.

The clinical trial protocol, each step of the data capture procedure and the handling of the data, including the final clinical trial report, will be subject to independent Quality Assurance activities. Audits may be conducted at any time during or after the trial to ensure the validity and integrity of the trial data. Representatives of the Quality Assurance unit from the Sponsor or a designated organization, as well as Health Authorities, must be permitted to access all trial documents and other materials at the site, including the Investigator Site File, the completed CRFs, all IMP and IMP accountability records, and the original medical records or files for each subject.

### **10.5 Changes to the Clinical Trial Protocol**

Changes to the clinical trial protocol will be documented in writing. Substantive amendments will usually require submission to the Health Authorities and to the relevant IEC/IRB for approval or favorable opinion. In such cases, the amendment will be implemented only after approval or favorable opinion has been obtained.

Minor (nonsubstantial) protocol amendments, including administrative changes, will be filed by the Sponsor and at the site. They will be submitted to the relevant IEC/IRB or to Health Authorities only where requested by pertinent regulations. Any amendment that could affect the subject's agreement to participate in the trial requires additional informed consent prior to implementation following the process as described in Section 9.2.

## **10.6 Clinical Study Report and Publication Policy**

### **10.6.1 Clinical Study Report**

After completion of the Phase I and Phase II of the trial, a Clinical Study Report will be written by the Sponsor in consultation with the Coordinating Investigator following the guidance in ICH Topic E3.

### **10.6.2 Publication**

Posting of data on the EU Clinical Trials Register and ClinicalTrials.gov sites is planned and will occur 12 months after the last clinic visit of the final trial subject or another appropriate date to meet applicable requirements.

The first publication will include the results of the analysis of the primary endpoints and will include data from all trial sites that provided evaluable data. The Investigator will inform the Sponsor in advance about any plans to publish or present data from the trial. Any publications and presentations of the results (abstracts in journals or newspapers, oral presentations, etc.), either in whole or in part, by Investigators or their representatives will require review by the Sponsor before submission. The Sponsor will not suppress publication, but maintains the right to delay publication in order to protect intellectual property rights.

## Appendix I: Contraceptive Guidance

In this clinical trial of children < 18 years of age, a female or male subject is considered to be of childbearing potential (and therefore required to use 2 highly effective methods of birth control) if, in the opinion of the Investigator, the subject is biologically capable of having children and is sexually active.

### Birth Control Methods Considered as Highly Effective

According to the Clinical Trials Facilitation Group (CTFG), “Recommendations related to contraception and pregnancy testing in clinical trials,” methods that can achieve a failure rate of less than 1% per year when used consistently and correctly are considered as highly effective birth control methods, such as:

- combined (estrogen and progesterone containing) hormonal contraception associated with inhibition of ovulation (oral, intravaginal, transdermal)
- progesterone-only hormonal contraception associated with inhibition of ovulation (oral, injectable, implantable)
- intrauterine device (IUD)
- intrauterine hormone-releasing system (IUS)
- bilateral tubal occlusion
- vasectomized partner
- sexual abstinence

 Hormonal contraception may be susceptible to interaction with the IMP, which may reduce the efficacy of the contraception method

 Contraception methods in the context of this guidance are considered to have low user dependency

 Vasectomised partner is a highly effective birth control method provided that the partner is the sole sexual partner of the woman of childbearing potential trial participant and that the vasectomized partner has received medical assessment of the surgical success

 In the context of this guidance sexual abstinence is considered a highly effective method only if defined as refraining from heterosexual intercourse during the entire period of risk associated with the study treatments. The reliability of sexual abstinence needs to be evaluated in relation to the duration of the clinical trial and the preferred and usual lifestyle of the subject.

### Contraceptive Guidance

Highly Effective Contraceptive Methods That Are User Dependent
Failure rate of < 1% per year when used consistently and correctly.
Combined (estrogen- and progestogen-containing ) hormonal contraception associated with inhibition of ovulation b oral intravaginal transdermal
Progestogen-only hormonal contraception associated with inhibition of ovulation b oral injectable
Highly Effective Methods That Are User Independent
Implantable progestogen-only hormonal contraception associated with inhibition of ovulation b Intrauterine device (IUD) Intrauterine hormone-releasing system (IUS) bilateral tubal occlusion
Vasectomized partner (A vasectomized partner is a highly effective contraception method provided that the partner is the sole male sexual partner of the WOCBP and the absence of sperm has been confirmed. If not, an additional highly effective method of contraception should be used.)
Sexual abstinence (Sexual abstinence is considered a highly effective method only if defined as refraining from heterosexual intercourse during the entire period of risk associated with the study drug. The reliability of sexual abstinence needs to be evaluated in relation to the duration of the study and the preferred and usual lifestyle of the participant.)
NOTES: a) Typical use failure rates may differ from those when used consistently and correctly. Use should be consistent with local regulations regarding the use of contraceptive methods for participants participating in clinical studies. b) Hormonal contraception may be susceptible to interaction with the study drug, which may reduce the efficacy of the contraceptive method. In this case 2 highly effective methods of contraception should be utilized during the treatment period and for at least 60 days after the last dose of study treatment.

**Avelumab**  
**MS100070-0306**

**Phase I/II study of avelumab in pediatric cancer subjects**

**[name]**

**Appendix III: Lansky and Karnofsky Performance Scales**

## Lansky Performance Scale

### Lansky play-performance scale for pediatric patients

This scale may be used with children age 1-16 who have any type of malignancy. It may be used for both inpatients & outpatients, and for patients undergoing active treatment as well as long-term follow-up. It is rated by parents based on their child's activity over the past week. Parents fill out the assessment based on the directions on the form, and the form is readministered over time to assess for changes in performance status.

An excerpt of the relevant directions for parents is as follows:

"Think about your child's play and activity over the past week. Think about both good days and bad days. Average out this period. Now read the descriptions and pick the one that best describes your child's play during the past week."

Rating	Description
100	fully active, normal
90	minor restrictions with strenuous physical activity
80	active, but gets tired more quickly
70	both greater restriction of, and less time spent in, active play
60	up and around, but minimal active play, keeps busy with quieter activities
50	lying around much of the day, but gets dressed; no active play, participates in all quiet play and activities
40	mostly in bed; participates in quiet activities
30	stuck in bed; needs help even for quiet play
20	often sleeping; play is entirely limited to very passive activities
10	does not play nor get out of bed
0	unresponsive

**Karnofsky Performance Scale**

The Karnofsky Performance Scale Index allows patients to be classified as to their functional impairment. This can be used to compare effectiveness of different therapies and to assess the prognosis in individual patients. The lower the Karnofsky score, the worse the survival for most serious illnesses.

**Appendix IV: Protocol Amendments and List of Changes**

## Amendment #1

Effective 15 September 2017 for all sites.

### Rationale

The rationale for this amendment is to make administrative changes and remove a statement included in the protocol.

### Major Scientific Changes

None.

### Administrative and Editorial Changes

Administrative changes:

- Change IND number from CCI [REDACTED] per request by the FDA for resubmission.
- Change of address for the coordinating investigator, effective 01 September 2017.
- Correct the name of the Sponsor for Canada from EMD Serono to Merck KGaA
- Update the name and address of the clinical trial lead on the Sponsor Responsible Persons Not Named on the Cover page.
- Update the version and date of the amendment throughout the document.

Editorial changes:

The following statement was inadvertently included in the protocol because of a copy-and-paste error; the statement has been removed in 3 places in the protocol: An independent imaging vendor will be engaged to read and interpret all computed tomography (CT)/magnetic resonance imaging (MRI) data. Responses will be evaluated using RECIST 1.1.

Comparison with Clinical Trial Protocol Version 1.0, 14 August 2017

Change	Section	Page(s)	Previous Wording	New Wording	Rationale
IND Number	Title page, Synopsis title page, signature pages of protocol lead, principal investigator, and coordinating investigator	Pages 1, 11, 107, 108, and 109	CCI	CCI	CCI
Change of title and address of coordinating investigator	Title page, Synopsis title page, Section 2, Coordinating investigator signature page	Pages 1, 11, 25, 108	PPD	PPD	Coordinating investigator's new location as of 01 September 2017
Change of sponsor address for Canada	Title page, Synopsis title page, Section 2	Pages 1, 11, 25	For all countries except the USA <del>and Canada</del> For sites in the USA <del>and Canada</del>	For all countries except the USA For sites in the USA	Incorrect sponsor address for Canada

Change	Section	Page(s)	Previous Wording	New Wording	Rationale
Update CTP version and date	Title page, signature pages of protocol lead, principal investigator, and coordinating investigator	Pages 1, 107, 108, and 109	<del>14 August 2017/Version 1.0</del> 15 September 2017/Version 2.0	15 September 2017/Version 2.0	Administrative change
Removed sentences about independent imaging vendor	5.1.1.1, 5.1.1.2, and 7.2.5	Pages 32, 38, and 72	<del>An independent imaging vendor will be engaged to read and interpret all computed tomography (CT)/magnetic resonance imaging (MRI) data. Response will be evaluated using REGIST 1.1.</del>	None	Copy-and-paste error—no independent read for secondary objections are planned.

Appendix I	Description of the Case Review for Assessment of Immune-Related AEs and Definition of Infusion Related Reactions	57

2 List of Abbreviations and Definition of Terms

ADA	Antidrug antibody
AE(s)	Adverse event(s)
AUC	Area under the serum concentration-time curve
AUC _{0-t}	Area under the serum concentration-time curve from time zero (= dosing time) to the last sampling time (t_{last}) at which the concentration is at or above the lower limit of quantification
AUC _{0-∞}	Area under the serum concentration-time curve from time zero (dosing time) extrapolated to infinity
AUC _τ	Area under the serum concentration-time curve over the dosing interval from $T_1=0$ h to $T_2=336$ h
BMI	Body mass index
BOR	Best overall response
BSA	Body surface area
C _{EOI}	Concentration at the end of the infusion
CI	Confidence Interval
C _{max}	Maximum serum concentration observed postdose
CIPD	Clinically Important Protocol Deviations
CL	Total body clearance
COVID-19	Coronavirus Disease 2019
CR	Complete response
CRF	Case report form
CSR	Clinical study report
CT	Computed tomography
CTMS	Clinical Trial Management System
CTP	Clinical trial protocol
C _{trough}	Minimum serum postdose trough concentration
CV	Coefficient of variation
DI	Dose intensity
DLT	Dose-limiting toxicity
DOR	Duration of response
ECG	Electrocardiogram
eCRF	Electronic case report form

eDISH	Evaluation of drug-induced serious hepatotoxicity
EOT	End of treatment
FAS	Full analysis set
GCP	Good Clinical Practice
GeoMean	Geometric mean
IAP	Integrated analysis plan
ICF	Informed Consent Form
ICH	International Council for Harmonisation
IPD	Important protocol deviation

LLOQ	Lower limit of quantification
Max	Maximum
Min	Minimum
MTD	Maximum tolerated dose
NAb	Neutralizing antibody
NCI-CTCAE	National Cancer Institute Common Terminology Criteria for Adverse Events
NE	Not evaluable
NR	No result
OR	Objective response
OS	Overall survival
PD	Progressive disease
PD-L1	Programmed death ligand 1
PFS	Progression-free survival

PK	Pharmacokinetic(s)
PP	Per protocol
PR	Partial response
PT	Preferred Term
RBC	Red blood cell
RDI	Relative dose intensity
RECIST 1.1	Response Evaluation Criteria in Solid Tumors version 1.1
RP2D	Recommended phase 2 dose
SAE(s)	Serious adverse event(s)
SDTM	Study data tabulation model
SCR	Screening analysis set
SD	Stable disease
SD	Standard deviation
SMC	Safety Monitoring Committee
SOC	System organ class
SOLD	Sum of longest diameters
t_{last}	Last PK sample at which the concentration is at or above the lower limit of quantification
$t_{1/2}$	Half-life
TEAE	Treatment-emergent adverse event
TNR	Titer no result
TTR	Time to response
ULN	Upper limit of normal
V_z	Apparent volume of distribution during the terminal phase
λ_z	Terminal first order (elimination) rate constant
τ	Dosing interval

3 Modification History

Unique Identifier for Version	Date of IAP Version	Author	Changes from the Previous Version
1.0	18 December 2017	PPD	NA First Version
2.0	22 June 2021	PPD	
Background: the avelumab EMA PIP has been modified and evaluation of avelumab monotherapy in pediatric patient has been terminated after Phase I of this study. Therefore, analysis of Phase II data will not be completed. The analyses described have been modified according to the needs of the Phase I reporting. All changes implemented in the IAP are listed below:
 
 • Section 6: Update trigger for Final Analysis to occur after all subjects have withdrawn from the trial, rather than 1 year after last End of Treatment visit • Section 7: Update to drop inclusion of analysis of gestational age and weight at birth; remove text indicating efficacy analysis will not be performed for Phase I • Section 8.2: Add specifics regarding tumor category subgroup analysis; specify all efficacy analyses will be performed overall and by tumor category • Section 9: Update text for last-alive date to match current IAP language • Section 10.1: Update disposition table to count subjects treated, rather than subjects enrolled; update disposition table to remove study "completion" category, include death and progressive disease as reason for study discontinuation; remove table of subjects by region and site • Section 10.2.2: Added section to specify COVID-19 protocol deviation listing • Section 11.1: Removal of gestational age, pooled geographic region, birth weight from demographics table • Section 11.2: Update to specify medical history details will be listed only. • Section 11.3: Update to remove site of primary tumor and add tumor category to disease history table • Section 11.4: Update to include all prior anti-cancer treatments on a single listing, rather than have three separate listings • Section 12: Update to remove prior medications table; include prior medications in concomitant medication listing • Section 13: Sections for and analyses of partial doses, infusion rate reductions, and infusion interruptions removed • Section 14.1: Added details regarding analysis of objective response; updated listings to include tumor assessment and reason for overall response of NE to a single listing, rather than separate listings • Section 14.2 and 14.3: Update to clarify that the analyses will not be conducted if no responders are observed • Section 14.4: Update to analyze PFS in weeks, not months; update to provide details on PFS analysis (add Kaplan meier estimates)

Unique Identifier for Version	Date of IAP Version	Author	Changes from the Previous Version
			
CCI
 
 Section 15.1: Update to specify that Analyses of DLTs is per SMC assessment Section 15.3.3: Update to drop listing of irAEs outside the on-treatment period; removal of table of IRRs leading to withdrawal of study treatment Section 15.4.1: Removal of summary statistics analysis of laboratory values; removal of liver function test table; removal of eDISH plot; removal of shift to worst grade table; removal of shift to worst value table Section 15.5: Removal of vital signs summary statistics table Section 15.6: Removal of ECG analyses. A listing only will be produced. Section 15.6.1: Removal of change from baseline table for quality of life assessments Section 16.1: Specify handling of samples collected outside of the specified time windows; Section 16.1.2: Specify use of PK analysis set; update to definitions of PK parameters to provide additional details Section 16.1.2.2: addition of section to describe planned PK outputs Section 16.2: Update to produce only one listing for immunogenicity data Section 16.3: Update to display biomarkers as box plots, rather than using summary statistics; drop summary of cytokines and circulating proteins Section 16.4: Update to listing description to drop flags for ADA status

4 Purpose of the Integrated Analysis Plan (IAP)

The purpose of this IAP is to document technical and detailed specifications for the final analysis of data collected for Phase I, the dose-finding portion, of protocol MS100070-0306. Results of the analyses described in this IAP will be included in the Clinical Study Report (CSR). Additionally, the planned analyses identified in this IAP will be included in regulatory submissions or future manuscripts. Any post-hoc or unplanned analyses performed to provide results for inclusion in the CSR but not identified in this prospective IAP will be clearly identified in the CSR.

The IAP is based upon section 8 (Statistics) of the trial protocol and protocol amendments and is prepared in compliance with International Council for Harmonisation (ICH) E9.

5 Objectives and Endpoints

	Objective	Endpoint	IAP section
Primary Objective	To evaluate the safety and tolerability of avelumab	
Primary Endpoint
 
 Occurrence and severity of treatment-emergent adverse events (TEAEs) \geq Grade 3 according to National Cancer Institute Common Terminology Criteria for Adverse Events (NCI-CTCAE) version 4.03 
Secondary Endpoints
 
 Vital signs (including blood pressure and heart rate) Occurrence and severity of TEAEs, AEs of special interest, and treatment-related AEs, and incidence of laboratory abnormalities as graded by NCI-CTCAE version 4.03 	
 15.2 Adverse Events 15.5 Vital Signs 15.2 Adverse Events
	To determine the recommended Phase II dose (RP2D) of avelumab in pediatric subjects 0 to < 18 years of age with solid tumors and lymphoma	
Primary Endpoint
 
 Dose limiting toxicities (DLTs) to determine RP2D 	15.1 Dose-Limiting Toxicities
Secondary Objective	To assess antitumor activity of avelumab by determining the ORR according to RECIST 1.1 and as adjudicated by the Investigator in pediatric subjects with solid tumors and lymphoma treated with avelumab	
Secondary Endpoint
 
 Confirmed BOR according to RECIST 1.1 and as adjudicated by the Investigator 	14.1 Confirmed Best Overall Response
	To assess progression-free survival (PFS) based on Investigator assessments, duration of response (DOR), time to response (TTR), and overall survival (OS)	
Secondary Endpoint:
 
 DOR, TTR, PFS per RECIST 1.1 and as adjudicated by the Investigator and OS 	
 14.2 Duration of Response 14.3 Time to Response 14.4 Progression Free Survival 14.5 Overall Survival
	To characterize the pharmacokinetics (PK) of avelumab	
Secondary Endpoint:
 
 Single- and multiple-dose PK profiles of avelumab (ie, C_{max}, AUC, $t_{1/2}$, and C_{trough}, as data permit) 	16.1 Pharmacokinetics
	To assess the immunogenicity of avelumab	
Secondary Endpoint:
 
 Immunogenicity as measured by avelumab anti-drug antibodies (ADA), including neutralizing antibodies (nAbs) 	16.2 Immunogenicity
	To evaluate programmed death ligand (PD-L1) expression; tumor infiltrating T-cell activity; T-cell population; and T-cell, B-cell and NK-cell numbers in tumor tissue at Baseline and at confirmed progression (if tumor tissue is obtained)	
Secondary Endpoint:
 
 Assessment of tumor PD-L1 expression; tumor-infiltrating T-cell activity; T-cell population; and T-cell, B-cell, and NK-cell numbers at Baseline and at confirmed progression (if tumor tissue is obtained) 	16.3 Biomarkers

	Objective	Endpoint	IAP section
	To measure changes in vaccination-related antibody concentrations (diphtheria, tetanus, and pneumococcal conjugate)	Secondary Endpoint: 
Vaccination-related antibody concentrations	16.4 Vaccination-related antibody concentrations

6 Overview of Planned Analyses

This document covers the avelumab standards for analyses of efficacy and safety. There are no interim analyses for efficacy planned for this trial, but ad hoc interim analyses may be conducted if necessary. There will be periodic safety review by the safety monitoring committee (SMC). The SMC will be responsible for reviewing the safety data and output containing the following information:

- The number and proportion of subjects in the DLT Analysis Set who experienced a DLT during the DLT evaluation period (first two cycles or 28 days of study treatment)
- The number and proportion of TEAEs experienced by subjects in the DLT Analysis Set during the DLT evaluation period
- The number and proportion of TEAEs \geq Grade 3 experienced by subjects in the DLT Analysis Set during the DLT evaluation period.

The SMC will also review patient profiles.

All final, planned analyses identified in the Clinical Trial Protocol and in this IAP will be performed after the last subject has completed his or her end of treatment visit or has been transferred off the trial, and all study data is in-house, all data queries are resolved, and the database is locked.

Statistical analyses will be performed using cleaned eCRF data as well as external data including laboratory data.

7 Changes to the Planned Analyses in the Clinical Trial Protocol

The statistical methods specified in this document are in accordance with protocol version 2.0 (dated 15 September 2017).

The PK Analysis Set definition in this IAP is slightly modified from the protocol. The protocol defines the PK Analysis Set as all subjects who complete at least 1 administration of avelumab and who provide at least 1 sample with measurable concentrations of avelumab (at least 1 predose and 2 postdose from 2 or more treatment cycles). In the IAP, we remove the specification in parentheses as the PK analysis will include any PK data obtained, and it is not necessary for a subject to have 1 predose and 2 post dose concentrations.

The immunogenicity analysis set definition in this IAP is slightly modified from the protocol. The protocol defines the immunogenicity analysis set as all subjects who complete at least 1 administration of avelumab, and who have provided a blood sample prior to any avelumab treatment and at least 1 post-treatment sample. In this IAP, we are only including subjects who have received any dose of avelumab and have at least one valid ADA result (including negative, positive-titer no result (TNR)). This change prevents exclusion of subjects with a missing baseline sample.

The wording of the PK, Immunogenicity, and Biomarker analysis sets is slightly modified from saying “subjects who complete at least 1 administration of avelumab” to “subjects who receive any dose of avelumab”. This is to clarify that subjects that receive any amount of study medication can be included in these analysis sets including those who do not complete the full dose.

8 Protocol Deviations and Analysis Sets

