## 8.4 Analysis Sets

**Full Analysis Set (FAS):** All subjects enrolled in the study and receive at least 1 dose of avelumab.

**Safety Analysis Set (SAF):** All subjects who receive at least 1 dose of avelumab. In this trial, the SAF = FAS.

**Per-Protocol (PP) Analysis Set:** A subset of the FAS; will include all FAS subjects who did not have any clinically important protocol deviations.

**DLT Analysis Set (Phase I only):** All subjects with data used for implementing the dose escalation schedule. These subjects will have received all trial treatment administrations in the DLT evaluation period (first 2 cycles of treatment) or stopped treatment because of DLTs in the DLT evaluation period.

**PK Analysis Set:** All subjects who complete at least 1 administration of avelumab and who provide at least 1 sample with measurable concentrations of avelumab (at least 1 predose and 2 postdose from 2 or more treatment cycles).

**Immunogenicity Analysis Set:** All subjects who complete at least 1 administration of avelumab, and who have provided a blood sample prior to any avelumab treatment and at least 1 post-treatment sample.

**Biomarker Analysis Sets:** All subjects who complete at least 1 administration of avelumab, and who have provided the appropriate blood/serum/plasma samples for biomarker assessments.

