8.2 Definition of Analysis Sets and Subgroups

Screening Analysis Set (SCR)

The screening analysis set includes all subjects who signed the informed consent.

Full Analysis Set (FAS)

The full analysis set (FAS) will include all enrolled subjects who receive any dose of avelumab.

Safety Analysis Set (SAF)

The safety analysis set (SAF) will include all enrolled subjects who were administered any dose of avelumab. Analyses performed on the safety set will consider subjects as treated. In this non-randomized study, the FAS and the SAF will be identical.

Dose Limiting Toxicity (DLT) Analysis Set

The DLT analysis set includes all subjects who meet either of the following criteria:

- Have received 100% of all planned doses of treatment during the DLT evaluation period (first 2 cycles of treatment) and have been followed for at least 28 days
- Have stopped treatment because of a DLT in the DLT evaluation period

Pharmacokinetic (PK) Analysis Set

The PK Analysis Set will consist of all subjects who receive at least one dose of avelumab, have no important protocol deviations or important events affecting PK, and provide at least one measurable post-dose concentration. Subjects will be analyzed according to the actual treatment they received. All PK analyses will be based on this analysis set.

Immunogenicity Analysis Set

The immunogenicity analysis set will include all subjects who receive any dose of avelumab and who have at least one valid ADA result (including negative, positive-TNR).

Biomarker Analysis Set

Biomarker analysis set will include all subjects who receive any dose of avelumab and who have provided at least one blood, serum, plasma, or tumor sample for biomarker assessments.

Table 1 summarizes the use of the analysis sets in the different analyses.

Table 1 Statistical Analysis by Analysis Set

Analyses	Screening Analysis Set	Full Analysis Set	Safety Analysis Set	DLT Analysis Set	PK Analysis Set	Immunogenicity Analysis Set	Biomarker Analysis Set
Baseline Characteristics	✓	✓	✓				
Prior and Concomitant Therapies		✓	✓				
Compliance and Exposure			✓				
Primary Endpoint			✓	✓			
Secondary Endpoint		✓			✓	✓	✓
CCI							
Safety			✓				

9 General Specifications for Data Analyses

[figure not shown]
Throughout this document “start date” is the date of first dose of study treatment.

Data handling after cut-off date:

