16.2 Immunogenicity (Secondary Endpoint)

Analysis Set: Immunogenicity analysis set

Blood samples for ADA analysis will be collected predose (within 2 hours prior to study treatment) during Cycles 1, 2, 3, 5, 7, 13, 19, 25, and every 6 cycles thereafter for as long as the subject is receiving study treatment; and at the 30-day Safety Follow-up Visit. If the sample is positive for ADA, it will be re-analyzed to determine the titer and tested for neutralizing capacity. The ADA results will be derived based on the algorithm in Table 6. Subjects will be characterized into different ADA categories based on criteria in Table 7.

Table 6 Algorithm for the Derivation of ADA Results

Sample Screen Result in SDTM	Confirmatory Result in SDTM	Titer Result in SDTM	ADA Result in ADaM
Negative	NA	NA	Negative
NR	NA	NA	NR
Positive	Negative	NA	Negative
Positive	NR	NA	NR
Positive	Positive	Number	Number
Positive	Positive	NR	Positive-TNR

NR = no result, NA = not applicable, TNR = titer no result.

Negative, number, or positive-TNR are valid results, while number and positive-TNR are considered as positive.

Table 7 Subjects Characterized based on ADA Results

Category	Definition	Subject at Risk (Denominator for Incidence)
Never positive	No positive results at any time point	Number of subjects with at least one valid result at any time point
Ever positive	At least one positive result at any time point	Number of subjects with at least one valid result at any time point
Pre-existing	A positive ADA result prior to treatment with avelumab	Number of subjects with valid baseline result
Treatment boosted	A positive ADA result prior to treatment with avelumab and the titer ≥ 8 *baseline titer while on avelumab treatment	Number of subjects with valid baseline and at least one valid post-baseline result
Treatment emergent	Not positive prior to treatment with avelumab and with at least one positive post-baseline result	Number of subjects with at least one valid post-baseline result and without positive baseline results (including missing, NR)
Transient positive	If treatment emergent subjects have (a single positive evaluation, or duration between first and last positive result <16 weeks) and last assessment not positive.	Number of subjects with at least one valid post-baseline result and without positive baseline results (including missing, NR)

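### The SAP drops the post-treatment sample requirement from the Immunogenicity Analysis Set without a reason, so the ever-positive and never-positive rows can include children with only a predose ADA result

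*SAP*

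**What the plan says.** **Protocol, Section 8.4.** The Immunogenicity Analysis Set consists of treated subjects "who have provided a blood sample prior to any avelumab treatment and at least 1 post-treatment sample". Both samples are needed.

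**SAP, Sections 7 and 8.2.** The set is redefined: "The immunogenicity analysis set will include all subjects who receive any dose of avelumab and who have at least one valid ADA result". Section 7 prints the old and new definitions and gives one reason: "This change prevents exclusion of subjects with a missing baseline sample".

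**SAP, Section 16.2.** The new set is named as the analysis set for immunogenicity. In Table 7, *never positive* is defined as "No positive results at any time point", and the denominator for both never and ever positive is "Number of subjects with at least one valid result at any time point". Table 9 does the same for neutralizing antibodies, using a valid ADA result at any time. Other rows are stricter. The denominator for *treatment boosted*, for example, is "Number of subjects with valid baseline and at least one valid post-baseline result". All categories are reported as counts and percentages, by dose level and overall.

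**The concern.** The stated reason covers a child whose baseline sample is missing. It does not cover the opposite case, a child who has a baseline result and nothing after it, yet the new definition admits that child too. Section 7 exists to explain departures from the protocol, and this part of the departure is left unexplained. The neighbouring PK set in SAP 8.2 was also relaxed, but it still requires a measurable post-dose concentration.

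A negative predose result shows that the child had no detectable antibody before treatment. It says nothing about a response to avelumab. Reporting that child as never positive suggests follow-up that did not take place. Immunogenicity is a named secondary endpoint and Phase I plans only 12 to 36 children, so one or two can visibly move a percentage. Protocol 8.5.3.5 also plans to compare serum concentrations between ever-positive and never-positive subjects. A baseline-only child could contribute Cycle 1 concentrations to the never-positive group without having been evaluable for a response.

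**Working it through.** The documents state no ADA rate and no expected number of baseline-only children, so there is no figure to reproduce. The check has two parts.

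**1. Trace a child whose only ADA result is a negative Cycle 1 predose sample.**

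| Row (SAP Tables 7 and 9) | Denominator requires | This child |
|---|---|---|
| Never positive | a valid ADA result at any time | counted as never positive |
| Ever positive | a valid ADA result at any time | in the denominator only |
| Pre-existing | a valid baseline result | in the denominator, properly |
| Treatment boosted (Table 7 only) | valid baseline and post-baseline results | not counted |
| Treatment emergent, transient, persistent | a valid post-baseline result and no positive baseline | not counted |

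For Table 9, the derivation in SAP Table 8 sets the neutralizing-antibody result to negative when the ADA result is negative. The same child is therefore never positive there too.

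**2. Size of the effect.** Let n be the children with any valid ADA result, m those with only a predose result, a the number of those m who are positive, and x the ever-positive children among the n − m who have a post-baseline result.

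- Ever-positive rate as the SAP defines it: (x + a)/n
- Rate among children with a post-baseline result: x/(n − m)
- If a = 0, the first is (n − m)/n times the second, a relative lowering of m/n.

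Here n = 12 and n = 36 are the ends of the planned Phase I size (protocol 5.1.1). The values of m, a and x are assumptions.

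| n | m | x | SAP rate (a = 0) | With a post-baseline result | Relative lowering m/n |
|---|---|---|---|---|---|
| 12 | 1 | 2 | 2/12 = 16.7% | 2/11 = 18.2% | 8.3% |
| 12 | 2 | 2 | 2/12 = 16.7% | 2/10 = 20.0% | 16.7% |
| 36 | 1 | 4 | 4/36 = 11.1% | 4/35 = 11.4% | 2.8% |
| 36 | 2 | 4 | 4/36 = 11.1% | 4/34 = 11.8% | 5.6% |
| 36 | 4 | 4 | 4/36 = 11.1% | 4/32 = 12.5% | 11.1% |

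If the baseline-only child is positive (n = 12, m = a = 1, x = 2), the direction reverses: (2 + 1)/12 = 25.0% against 2/11 = 18.2%.

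Treatment-emergent incidence is x/(n − m) under the SAP as written, if no child has a positive baseline. With n = 12, m = 2 and x = 2 it is 2/10 = 20.0%, the same before and after any change to the ever/never rows.

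**How likely is m > 0?** Protocol Table 2 and Section 7.6.3 schedule ADA samples at Cycle 2, at End of Treatment and at the 30-day visit. A baseline-only child must lack a valid result at all of them. Phase I needs at least 12 DLT-evaluable children (protocol 5.1.1.1.6), who either received every dose in the first two cycles or stopped for a DLT. If only 12 children were treated, each would have reached the Cycle 2 dose or stopped for a DLT, so m = 2 of 12 is unlikely. Children who leave early for other reasons are replaced (protocol 5.1.1.1.1). They remain treated subjects, but they also enlarge n.

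**The case against.** The strongest case on the other side has four parts.

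- *Each row has its own risk set by design.* Ever positive includes pre-existing antibodies, so it is not purely a measure of response to avelumab, and a denominator of any valid result matches that definition. This is fair: different denominators within one table are not an error in themselves. It does not make never positive informative for a child who was not sampled after dosing.
- *The contrast with the protocol is partly inferred.* Protocol Table 7 uses the same denominator wording for these two rows, and protocol 8.5.3.5 names no analysis set for that table. That stands. What the SAP removed is the restriction in the analysis set. SAP 16.2, unlike the protocol, ties its tables to that set explicitly.
- *The change is disclosed.* Both definitions are printed in Section 7. That is true, but the reason covers only one of the two requirements that were dropped.
- *The number is small.* The sampling schedule supports this, as do the eligibility rules, which require a life expectancy of at least 3 months and exclude rapidly progressive disease.

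A reader might also infer that ADA incidence in general is diluted, or that a child with only a predose result is always scored never positive. The documents support neither. The treatment-emergent, transient, persistent and boosted rows already require a post-baseline result, and a baseline-only child with a positive result is ever positive and raises that rate. Nor do the documents make ever positive the leading immunogenicity result.

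**Conclusion.** The point holds in a limited form. The SAP no longer requires a post-treatment sample and gives no reason for that. Two descriptive rows in each of Tables 7 and 9 can therefore include children who were never evaluable for a response to avelumab. Baseline-only negative children lower the ever-positive rate by m/n, for example 2.8% in relative terms for 1 of 36 or 8.3% for 1 of 12. Baseline-only positive children raise it. These sizes rest on assumed values of m, which the documents do not give and which is probably small. A lowering of a third (4 of 12) is arithmetically possible but implausible given the sampling schedule and the requirement for 12 DLT-evaluable children. The incidence of treatment-emergent, transient, persistent and boosted antibody is not affected.

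**What to change.** - Keep the Immunogenicity Analysis Set as in SAP 8.2, so that children with a missing baseline stay in. Leave the pre-existing rows on subjects with a valid baseline result. Shrinking the whole set is unnecessary and would put the pre-existing rows outside the set that SAP 16.2 uses.
- In Tables 7 and 9, require at least one valid post-baseline ADA result in the denominators for ever positive and never positive.
- Show children with only a baseline result as a separate count.
- State in Section 7 that the set no longer requires a post-treatment sample.
- While editing Section 16.2, reconcile its ADA sampling schedule with the protocol. The SAP text omits the End of Treatment sample that the protocol collects.

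**Cost.** A few phrases and no new data. The ever-positive rate may change slightly. A baseline-only positive child would appear under pre-existing but not under ever positive, which needs a footnote.
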